**Figure 7. Lung Nodule Management Protocol** 

## C2. Participant Inclusion and Exclusion Criteria

## C2.1 Inclusion Criteria

- Women or men age 55 to 80 years.
- Current or former smokers. A former smoker is defined as one who has stopped smoking for one or more years.
- An estimated 6-year lung cancer risk of ≥1.51% based on the PLCOm2012 risk prediction model
  or ≥ 30 pack-years smoking history (pack-year is defined as number of pack of cigarettes smoked per
  day multiply by the number of years smoked. If a participant stopped smoking for 6 months or more
  and then restarted smoking again, the time will be subtracted from the total duration of smoking in
  0.5-year increments)
- ECOG performance status 0 or 1.
- Capable of providing, informed consent for screening procedures (low dose spiral CT)

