## **C3.** Number of Participants

2,000 participants will be accrued from Vancouver and 2,000 participants will be accrued from 4

centers in Australia (Brisbane, Sydney, Melbourne, Perth) over 24 months. Pending institutional approval, it is anticipated that an additional 4,000 participants will be recruited from Denmark and Italy for a total of 8,000 participants. Both men and women and members of all races and ethnic groups are eligible for this trial. The rationale for the sample size is described below.

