## C4.2 Eligibility assessment process (Figure 2)

C4.2.1 People interested in participating in the study will telephone the study centre (free call number) and speak with the research coordinator/assistant or will leave contact details for return calls. People approached through direct mail out will also be given a telephone number to call or will be provided with a written form (including contact details) and reply-paid envelope to return to the study centre. The research coordinator at each study centre will conduct an initial telephone eligibility assessment using an innovative web-based lung cancer risk assessment tool (PLCOm2012 developed by [name]

[name]). This tool is available as an iPhone app or iPad app or accessed online. This tool can automatically display the lung cancer risk and indicate whether a person is eligible for LDCT screening according to the PLCOm2012-risk≥0.0151 selection criteria or the USPSTF criteria (Figure 2).

- C4.2.2 Those who meet the PLCOm2012 1.51%/6 years lung cancer risk criteria or the USPSTF screening criteria (current smokers who have smoked at least 30 pack-years and former smokers who have smoked 30 pack-years and who have stopped smoking for less than 15 years) will be asked a further series of questions to assess eligibility based on all inclusion/exclusion criteria. Those who are eligible will be invited for a face-to-face meeting to verify smoking history and smoking status (for former smokers by urinary cotinine or exhaled carbon monoxide), inclusion/exclusion criteria, explanation of the risks and benefits of LDCT screening. Participants who are unable to travel twice will have their smoking status verified on the day of the CT scan. Informed consent will be obtained for the main study and for optional studies (e.g., outdoor and household air pollution exposure and blood specimen collection) before the CT scan.
- C4.2.3 A study number will be assigned. Those not eligible for screening will be assigned a study number with additional code to denote ineligibility.
- C4.2.4 Informed consent will be obtained using the attached study patient information and consent forms (Appendix XXX)
- C4.2.4.1 Eligible participants who have provided informed consent will be invited to undergo CT screening and will be invited to consent to be involved in sub-studies.

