# **C5.0 Optional Sub-Study at the Vancouver Site**

The modified Pan-Canadian Early Detection of Lung Cancer risk assessment questionnaire (Figure 2) plus an outdoor and domestic air pollution exposure questionnaire (Appendix 1) will be administered to all newly diagnosed lung cancer patients (estimated to be 1,400 patients over two years) who will be attending the Vancouver Cancer Center of the BC Cancer Agency or the Thoracic Surgery Department of the Vancouver General Hospital (VGH). The VGH Thoracic Surgery Unit is one of four thoracic surgery centers for surgical treatment of lung cancer patients in the entire 4.6 million population in British Columbia. From the risk assessment tool, we will determine the relative sensitivity of the PLCOm2012-risk ≥1.51% threshold versus the USPSTF screening criteria to identify lung cancer patients who are ever smokers.

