C13.3 To determine the incremental value of air pollution for lung cancer risk assessment versus the PLCOm2012 model, newly diagnosed lung cancer patients (both ever-smokers and never-smokers) and the Lung Screening Study participants (ever-smokers) in the Vancouver site will be used to test if there is a significant difference in the pollution index between those with and without lung cancer and those who meet the PLCOm2012 6-year lung cancer risk threshold ≥0.0151 versus those who don't. We will externally validate any resultant risk prediction model using the Canadian Partnership for Tomorrow Project (CPTP) cohorts, the Canadian Communities Health Survey (CCHS) data linked to provincial cancer cancer incidence registries (Table 2), as well as the on-going 10,000 screening cohort from the National Taiwan University to determine the predictive performance (discrimination and calibration) of the model overall, and where numbers permit, in subsets and ethnic subgroups of the population. The CPTP and CCHS data linked to cancer registry outcomes provide ideal data for our efforts to validate the PLCO risk models and lung cancer screening selection criteria in Canadian settings, and to

potentially improve them. These data include prospective follow-up data which provide estimation of true risks based on incidence data (probability of lung cancer in a defined population at risk per defined time period).

We anticipate well over 1,700 lung cancers from the CPTP and CCHS cohorts. To minimize over-fitting of any new model, a rule of thumb suggests that 10-20 outcomes be present per predictor variable in the model. We expect all new models to have 15 or fewer predictors and thus do not expect serious problems with over-fit. We will also use bootstrap methods to estimate model *optimism*.

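### The Vancouver air-pollution test in C13.3 compares cases that include never-smokers with risk-selected ever-smoker participants, without conditioning on PLCOm2012, so it does not measure incremental value over that model

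*Protocol*

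**What the plan says.** Protocol C13.3 gives the purpose: "To determine the incremental value of air pollution for lung cancer risk assessment versus the PLCOm2012 model". The groups are "newly diagnosed lung cancer patients (both ever-smokers and never-smokers) and the Lung Screening Study participants (ever-smokers) in the Vancouver site", and the plan is to "test if there is a significant difference in the pollution index between those with and without lung cancer". A second comparison follows in the same sentence: people at or above the 0.0151 PLCOm2012 threshold against those below it. No adjustment, stratification or restriction is attached to either comparison.

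The two groups are recruited differently:

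- **Cases (C5.0).** The questionnaires "will be administered to all newly diagnosed lung cancer patients" at two Vancouver institutions, "estimated to be 1,400 patients over two years". No age or risk limit is given. For the relative-sensitivity comparison, C5.0 looks at ever-smokers within this same series; C13.3 explicitly includes the never-smokers.
- **Screening participants (C2.1, C3, C4.2.2).** "2,000 participants will be accrued from Vancouver". They are ever-smokers aged 55 to 80. C2.1 requires "An estimated 6-year lung cancer risk of ≥1.51% based on the PLCOm2012 risk prediction model" or, alternatively, at least 30 pack-years. C4.2.2 takes forward "Those who meet the PLCOm2012 1.51%/6 years lung cancer risk criteria or the USPSTF screening criteria".

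C13.3 then goes on to a prediction model, bootstrap optimism and external validation in other cohorts. It discusses the gain in AUC from added predictors and plans NRI and decision curve analysis.

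**The concern.** Incremental value over PLCOm2012 is a conditional question: among people with the same PLCOm2012 risk, does the pollution index still separate those who have lung cancer from those who do not? The named test is unconditional, and its groups differ by design in smoking status, age limits and risk selection.

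Never-smoker cases may differ from ever-smokers in residence, migration and fuel use. The index is time-weighted from intensity and duration of exposure (C12), so an age difference may also move it. A difference in the index could then reflect who was recruited rather than what pollution adds in ever-smokers, the population the selection model serves.

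The threshold comparison has a separate weakness. It shows how the index correlates with the existing score, and such a correlation can exist with no added predictive value. At stake is whether a significant Vancouver result is read as support for adding pollution to the model.

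**Working it through.** C13.3 gives no sample size, power or effect size for this test, so there is no figure to reproduce. Three checks were made.

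**1. Who is below the threshold among those screened?** Inputs from C13.1: 85.3% USPSTF-positive, 77.8% PLCOm2012-positive, correlation -0.222.

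- Both = 0.853 × 0.778 - 0.222 × √(0.853 × 0.147 × 0.778 × 0.222) = 0.664 - 0.033 = 0.631.
- Neither = 1 - 0.853 - 0.778 + 0.631 = 0.000.
- Below 1.51% = 1 - 0.778 = 22.2%, about 444 of 2,000.

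On the plan's own figures, screened participants below the threshold are there because of the smoking rule. Four of the model's eleven inputs are smoking variables (Project Summary), and C13.3 does not say how never-smoker cases are to be placed in this contrast.

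**2. False-positive rate of the unconditional test.** Inputs: 1,400 cases (C5.0); 2,000 participants (C3, an upper bound because the questionnaire is optional); two-sided alpha 0.05 (stated for C13.1, assumed to carry over). Assumed, because the documents do not give them: never-smoker share of cases f, and mean difference d (never minus ever) in SD units. Pollution has no effect within ever-smokers.

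- SE = √(1/1400 + 1/2000) = 0.0348 SD.
- z = f × d / SE.
- Rate = 1 - Φ(1.96 - z) + Φ(-1.96 - z).
- Example, f = 20% and d = 0.3: z = 0.06/0.0348 = 1.72, rate 0.406.

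| f | d = 0 | 0.1 | 0.2 | 0.3 | 0.5 |
|---|---|---|---|---|---|
| 10% | 0.050 | 0.059 | 0.089 | 0.138 | 0.300 |
| 20% | 0.050 | 0.089 | 0.209 | 0.406 | 0.819 |
| 30% | 0.050 | 0.138 | 0.406 | 0.733 | 0.990 |

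With half the numbers (700 against 1,000, SE 0.0493), f = 20% and d = 0.3 give 0.230.

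**3. Simulation of the remedy.** There were 400 replicates per scenario, with pollution null given PLCOm2012 and participants at or above 1.51%. Simulation error is about ±0.02 near 0.05. In the rows below, c is the assumed correlation of the index with the PLCOm2012 log-odds.

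| f, d, c | All cases, unadjusted | Ever-smoker cases, unadjusted | Ever-smoker cases at ≥1.51%, adjusted for log-odds |
|---|---|---|---|
| 20%, 0, 0 | 0.048 | 0.043 | 0.040 |
| 20%, 0.3, 0 | 0.425 | 0.045 | 0.058 |
| 20%, 0.5, 0 | 0.828 | 0.070 | 0.065 |
| 20%, 0.3, 0.2 | 0.160 | 0.065 | 0.053 |
| 0, 0, 0.2 | 0.078 | 0.078 | 0.035 |

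The adjusted analysis is compatible with 0.05 throughout. The fourth row shows that correlation with the score can also shrink the distortion, so its size is not fixed even for a given f and d. The last row suggests that restriction to ever-smokers alone may not suffice when the index correlates with the score.

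**The case against.** The strongest reply is that one sentence is being read as the whole plan. C13.3 continues to a prediction model, AUC gain, NRI, decision curves and external validation. A reader might infer that incremental value is never tested; the documents do not support that. The point holds for the named Vancouver test. It reaches the later measures only in that the section does not say whether they would avoid the same mismatched groups.

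A second reply is that C13.3 is silent on adjustment rather than ruling it out, and that covariates are commonly left to an SAP. Smoking history and the other model inputs are collected, so adjustment is possible. That is fair as to covariates. But the group composition and the two contrasts are stated, and as stated they do not match the stated purpose.

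Third, a higher index in never-smoker cases could be partly real: A4 cites relative risks of 1.22 to 2.66 for household coal and wood burning in never-smokers. This stands, but an effect confined to never-smokers would still not show added value in a model for selecting ever-smokers.

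Fourth, the text following C4.2.2.3 allows air pollution surveys among ineligible people and decliners, so lower-risk respondents might exist. It says only that consent may be sought, and C13.3 names only screening participants, described as ever-smokers.

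Finally, no rule carries a significant difference into a selection model, and any resulting model is to be externally validated. That limits the consequence. However, C12 presents the detailed residential history as particular to this study, and the protocol does not say that the validation cohorts hold the index.

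**Conclusion.** The concern holds for the Vancouver test as written. Its groups differ by design in smoking status and in age and risk selection, it states no conditioning on either, and its purpose is incremental value over PLCOm2012. The threshold contrast cannot supply that evidence.

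The size is illustrative. With 20% never-smokers among cases and full uptake, the false-positive rate runs from 5% at zero shift to 82% at 0.5 SD. Neither share nor shift is in the documents. A reader might take one of the high percentages as the error rate of this study, which the documents do not support: with no shift there is no inflation from this source, and with fewer respondents there is less.

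Nor should the participants be described as all above the PLCOm2012 threshold, since about 22% would fall below it on the plan's own assumptions. They share admission by at least one rule.

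This is worth correcting before analysis, but it concerns an optional single-site sub-study and leaves the primary objectives untouched.

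**What to change.** Reword C13.3 as follows:

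- Make the primary Vancouver test the association of the pollution index with lung cancer in ever-smoker cases and ever-smoker participants over the same age and risk range, in a logistic model that already contains the PLCOm2012 log-odds.
- Report never-smoker cases separately and descriptively.
- Label the threshold contrast as descriptive, not as evidence of incremental value.
- Base any AUC or NRI claim on this ever-smoker comparison, or on cohorts where the index is available.

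No new data are needed. The cost is fewer cases. If 20% are never-smokers (assumed), 1,400 × 0.8 = 1,120 remain and the SE of a simple difference rises from 0.0348 to √(1/1120 + 1/2000) = 0.0373 SD, about 7%. Matching the risk range removes more. A1 reports that under 40% of US patients would meet USPSTF; the share meeting either rule is not given. If only 40% (560) remained, the SE would be √(1/560 + 1/2000) = 0.0478 SD, about 37% larger. The common risk range must also be defined explicitly, because C2.1 states the smoking rule without a quit-time limit whereas C4.2.2 uses USPSTF, which has one.

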## **Project Summary**

Background. The cost-effectiveness of a population-based lung cancer screening program with low-dose computed tomography (LDCT) to reduce lung cancer mortality is strongly influenced by the sensitivity and specificity of the selection criteria for screening. Retrospective analysis by [name] and coworkers showed that the PLCOm2012 lung cancer risk prediction model using 7 non-smoking and 4 smoking variables detects 7.6% more lung cancer and samples 8.7% fewer people compared to the US Preventive Services Task Force (USPSTF) screening inclusion criteria based on age and smoking history alone. The sensitivity and specificity of PLCOm2012 versus USPSTF screening criteria to select smokers for lung cancer screening has not been prospectively evaluated in the general population.

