Although outdoor and household air pollution account for an estimated 29% of lung cancer deaths worldwide, none of the 17 lung cancer risk prediction models published so far has included outdoor and/or household pollution as one of the risk variables. A prospective analysis of data from 17 cohort studies (312,944 participants) based in nine European countries by the European Study of Cohorts for Air Pollution Effects showed a statistically significant association between the risk for lung adenocarcinoma and PM10 (hazard ratio [HR] of 1.51 (1.10-2.08) per 10  $\mu$ g/m³) and HR of 1.55 (1.05-2.29) per 5  $\mu$ g/m³ for PM2.5.³6 In Canada, a case-control study of 2390 incident lung cancers from eight different provinces, estimated an elevated odds ratio of 1.29 (95% confidence interval = 0.95-1.76) per

per 10 μg/m³ increase in PM2.5. Worldwide, around 2.4 billion people use traditional biomass fuels for household cooking or heating. The ORs for lung cancer risk with biomass for cooking and/or heating were 1.21 (95% CI 1.05 to 1.39) for men and 1.95 (95% CI 1.16 to 3.27) for women in studies with adequate adjustment and a clean reference category. With global migration patterns and a multiethnic society, it is important to examine the role of outdoor and household air pollution as part of a lung cancer risk prediction model. The Canadian Partnership Against Cancer Expert Panel on Identifying Individuals at High Risk for Lung cancer Screening made the recommendation that air pollution should be considered for inclusion in existing lung cancer risk prediction models. As an optional study, we will offer the participants to answer a detailed epidemiologic questionnaire to collect information on outdoor and household air pollution exposures in addition to history regarding smoking habits, family history of lung cancer, personal history of cancer, chronic obstructive pulmonary disease, occupation, symptoms and medications (Appendix 1).

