A unique feature of this study is the ability to collect detailed residential history within Canada and prior residence outside of Canada (for foreign born immigrants) as well as household exposures from cooking and heating with solid fuels such as coal. From a full address, or just a city or street name – a coordinate value will be obtained from Google Maps (www.maps.google.ca) for each place of residence. The coordinates will be used for mapping of the long term air pollution exposure level (PM2.5) using satellite observations. We have previously developed global high resolution models of outdoor air pollution levels that have been successfully applied to epidemiologic analyses including cancer mortality in China and Canada. A time weighted air pollution exposure index will be developed from the intensity and duration of exposure similar to tobacco smoke exposure. We will also use our questionnaire to identify those who used solid fuels for cooking or heating and to generate exposure duration for household air pollution exposure. Since information on radon exposure based upon measurements from individual homes is usually lacking, we will test inclusion in the prediction model of estimated radon exposure based on risk prediction maps in a sensitivity analysis only.

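### C13.3 tests the added value of air pollution partly by comparing the pollution index across the PLCOm2012 threshold, a contrast that reflects correlation with PLCO risk and not added prediction of lung cancer.

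*Protocol*

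**What the plan says.** The purpose in Protocol C13.3 is explicit: "To determine the incremental value of air pollution for lung cancer risk assessment versus the PLCOm2012 model". Newly diagnosed lung cancer patients and the Vancouver screening participants are to be used to test for a "significant difference in the pollution index between those with and without lung cancer and those who meet the PLCOm2012 6-year lung cancer risk threshold". The second contrast is completed as "those who meet the PLCOm2012 6-year lung cancer risk threshold ≥0.0151 versus those who" do not meet it. C13.3 gives no effect size, power or adjustment for either contrast.

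The Project Summary describes PLCOm2012 as "using 7 non-smoking and 4 smoking variables". Section A4 says that "none of the 17 lung cancer risk prediction models published so far has included outdoor and/or household pollution as one of the risk variables". Section C12 describes the exposure measure: "A time weighted air pollution exposure index will be developed from the intensity and duration of exposure similar to tobacco smoke exposure".

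The rest of C13.3 refers to external validation of any resulting model (discrimination and calibration), gain in AUC, net reclassification improvement (NRI) and decision curve analysis.

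**The concern.** Incremental value means that pollution predicts lung cancer beyond what PLCOm2012 already predicts. Grouping people by whether they pass the PLCOm2012 threshold brings in no lung cancer outcome. The contrast then asks whether exposure is associated with the score, which is a different question and in part the reverse one. An index that only duplicates information already in the score can give a clear difference. An index that is independent of the score, and so has the most to add, need not.

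At stake is interpretation. The contrast is listed under the stated purpose of determining incremental value, so a significant result could be cited as support for adding pollution when it shows only shared dependence on baseline characteristics. A null result could be cited against a real independent risk factor.

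**Working it through.** The plan gives no figure for this contrast, so there is nothing to reproduce. The check is a reading of what enters each contrast, followed by illustrative calculations.

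**What enters each contrast**

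| Contrast in C13.3 | Variables used | Conditions on PLCO risk? |
|---|---|---|
| Index, lung cancer vs none | index, outcome | No, as worded |
| Index, threshold met vs not met | index, PLCO status | Not applicable: PLCO status is the grouping |

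Neither is an association of the index with lung cancer given PLCO risk.

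**Screening participants alone, no pollution effect**

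Inputs:
- "2,000 participants will be accrued from Vancouver" (C3).
- 77.8% PLCO-positive, the planning figure in C13.1: 0.778 × 2,000 = 1,556 positive and 444 negative.
- Two-sided alpha 0.05, stated for C13.1; C13.3 states none.
- Assumed: index and PLCO score are standard bivariate normal with correlation ρ.

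Formulas:
- Cut-point c with P(Z > c) = 0.778: c = −0.765, density φ(c) = 0.2976.
- Mean difference in the index = ρ × φ(c) / (0.778 × 0.222) = 1.723ρ.
- Standard error = √(1/1,556 + 1/444) = 0.0538.
- Expected z = 1.723ρ / 0.0538 = 32.0ρ. Rejection probability ≈ Φ(z − 1.96) + Φ(−z − 1.96).

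| ρ (assumed) | Expected z | Rejection, closed form | Range including simulations |
|---|---|---|---|
| 0 | 0 | 5.0% | about 5% |
| 0.05 | 1.60 | 36% | 31-36% |
| 0.10 | 3.20 | 89% | 89-91% |
| 0.15 | 4.80 | 99.8% | above 99% |

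**Cases and screening participants pooled**

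Inputs:
- Cases "estimated to be 1,400 patients over two years" (C5.0), with 2,000 non-cases.
- Assumed: log-odds slope of 1.0 per SD of PLCO log-risk, and threshold at its 35th percentile in the source population.
- Odds ratio 1.29: A4 cites this per 10 µg/m³ of PM2.5. Applying it per SD of the index is an assumption.

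Rejection rates over 400 simulated data sets per row:

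| Scenario | Threshold contrast, pooled | Threshold contrast, non-cases only | Unadjusted case vs non-case | Index adjusted for PLCO log-risk |
|---|---|---|---|---|
| ρ = 0.2, no pollution effect | 100% | 100% | 100% | 5% |
| ρ = 0, odds ratio 1.29 per SD | 52% | 6.75% | 100% | 100% |
| ρ = −0.2, log odds ratio 0.2 per SD | 100% | 100% | 5% | 100% |
| ρ = 0, no effect | 6% | 5% | 6% | 7% |

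In the second row, other simulations with different set-ups put the pooled rejection rate as low as 31%; with 22.2% of the non-cases PLCO-negative it was 46%. The pooled response arises because cases are over-sampled. They carry more exposure and are more often PLCO-positive, so exposure and PLCO status become associated in the sample though they are independent in the population.

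The threshold contrast follows ρ and the sampling. Only the adjusted outcome model separates no added value (row 1) from added value (rows 2 and 3). The unadjusted case contrast errs in rows 1 and 3.

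**The case against.** **Valid methods are already named.** C13.3 goes on to AUC, NRI, decision curves and external validation, all of which use the outcome. This stands. A reader might infer that the protocol has no sound way to assess incremental value, and the text does not support that. But those steps do not make the threshold contrast informative, and it is still listed as a test for that purpose.

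**The outcome is not wholly absent.** If the newly diagnosed patients are pooled in, the sample is selected on the outcome and the contrast does respond to a pollution effect. This also stands. A reader might conclude that the contrast can reject only at the alpha level however strongly pollution predicts cancer. That holds for screening participants alone and fails in the pooled sample. The response is a product of case sampling, however, and not a measure of added prediction.

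**No decision hangs on it.** C13.3 does not say that a significant result puts pollution into the model or that a null result keeps it out. Correct; the harm described is a risk of misreading, not a stated rule.

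**The index need not rise with age.** A cumulative index of intensity and duration would tend to, and that would build in a correlation with PLCO risk. C12 gives no formula, and a time-weighted average need not behave that way. An age-driven difference is therefore possible but not established, and the calculations above do not rely on it.

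**The sentence may mean a cross-classification** of cancer status within PLCO strata, which would use the outcome. That is possible, but the wording sets those above the threshold against those below it as a contrast of its own. If strata were meant, the sentence needs rewording anyway.

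**Conclusion.** The point holds. As worded, the threshold contrast in C13.3 cannot show incremental value, because it reports the correlation between pollution and PLCO risk, with an added case-sampling artefact in a pooled sample. Among 2,000 screening participants even a correlation of 0.10 makes it significant in about nine runs in ten with no pollution effect. The companion contrast by lung cancer status, if unadjusted, does not isolate added value either.

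That the contrast does not answer the question follows from its definition. The rejection rates rest on assumed correlations, normal distributions, a PLCO slope of 1.0 and an odds ratio of 1.29 applied per SD; none of these is a protocol estimate for this index.

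The reach is limited. This is one comparison in an optional Vancouver sub-study; the primary objectives, the sample size and the later outcome-based methods are unaffected.

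**What to change.** In C13.3, label the comparison by PLCOm2012 status as a description of how exposure relates to PLCO risk, or delete it. Base the incremental-value test on lung cancer status modelled on the PLCOm2012 linear predictor, with and without the pollution index. If analysis within PLCO strata was intended, say so and add a pollution-by-PLCO-status interaction to that model.

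This changes one sentence and needs no new data. The cost is one fewer test, and estimates in the PLCO-negative stratum will be imprecise (about 444 of 2,000 screening participants at the C13.1 proportion).
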